Baseline measurements will be undertaken within 30 min after extubation. Subsequently, all patients will be assessed for downward titration of respiratory support at 1, 2 hours, and then, every 4 hours after extubation. Respiratory physiological follow-up will extend up to 48 hours after extubation. At the aforementioned follow-up time points, data collection will include SpO_2 , respiratory rate, $\text{PaO}_2/\text{FiO}_2$, comfort as regards dyspnea and respiratory support modality [visual analogue scale (VAS) score²⁴], accessory muscles' use, arterial pressure and heart rate, vasopressor support, and core body temperature. Fluid balance of the first 24 and 48 hours postextubation will also be recorded.

Gradual weaning from NHF support will include FiO_2 downward titration to 50%, followed by downward titration of gas flow to 30 L/min, aiming at a final wean-off goal of $\text{FiO}_2=0.4$ and gas flow=20 L/min (unless the attending physician decides to turn the patient to a Venturi mask from a gas flow of 25 to 30 L/min).¹² If at NHF $\text{FiO}_2=0.4$ and flow rate=20 L/min, pulse oximeter-measured, peripheral oxygen saturation (SpO_2) and respiratory rate can be respectively maintained above 92% and within 12 to 20 breaths/min for at least 2 hours, patients will be switched to conventional oxygen therapy with a Venturi mask ($\text{FiO}_2=0.4$). In the control group, downward titration of support will be aimed at Venturi mask $\text{FiO}_2=0.4$. Patients of all groups fulfilling the aforementioned SpO_2 /respiratory rate criteria for at least 4 hours while receiving an FiO_2 of 0.4 via a Venturi mask will be considered for cardiothoracic ICU discharge.

During the postoperative/postextubation period, respiratory support may be escalated to maintain an SpO_2 of >92% and a respiratory rate of 12-29 breaths/min. Changes in respiratory support level and/or modality will ultimately made and/or approved by the patients' primary attending physicians.

Study Eligibility Criteria

- Adult Cardiac ICU patients.

- Age of more than 18 years.
- After elective or urgent cardiac surgery.
- Successful spontaneous breathing trial with T-piece and an FiO_2 of 60% (eligibility criterion for extubation).
- $\text{PaO}_2/\text{FiO}_2$ of less than 200 mmHg (moderate hypoxemia – normal value \sim 500 mmHg)
- Hemodynamically stable, defined as systolic arterial pressure within 90 to 160 mmHg with or without low-to-moderate vasopressor support.

Exclusion Criteria:

‡, In SG 2, support escalation should be initially accomplished by gas flow increase of 5-10 L/min; this can be followed by FiO₂ titration to an SpO₂ of more than 92%.

[figure not shown]
§, Regarding CG patients on nonrebreathing mask due to respiratory support escalation, an FiO₂ reduction from 0.9 to 0.6 via a Venturi mask should be performed for escalation reversal.

**, Reversal of respiratory support escalation is defined as return to initial (or lower) FiO₂ and/or gas flow for at least 4 hours.

Applicable definition of hypoxemia: SpO₂ drop to 92% or less for at least 5 min.

SOP FOR THE RATING OF THE LEVEL OF BREATHING COMFORT

At the specified time points of patient follow-up: Investigators should use the below-displayed comfort/discomfort visual analogue scale to help patients rate the level of their breathing comfort. The following simple question should be asked: How would you rate the level of your breathing comfort starting from 0 (maximum discomfort – feeling unable to breathe) to 10 (maximum comfort – feeling capable of smooth and steady breathing, without having even the slightest difficulty).

Contents

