Studies applying NHF immediately after extubation in cardiac surgery patients revealed better oxygenation and less need for advanced methods of respiratory support compared to conventional oxygen devices^{25,26}, and similar results compared to noninvasive ventilation²⁷. However, Zochios et al,²⁸ summarized all the available up to date data of NHF compared to conventional oxygen devices and non-invasive ventilation in patients undergoing cardiothoracic surgery and they did not find any further benefit by NHF use. The aforementioned discordant results could be explained by the differences in the studied populations and NHF flow settings. The proposed initial flow rate differs among the studies, with some authors^{2,4} suggesting initial lower flows (35-40 L/min) that will be better tolerated by the patients and others suggesting initial maximal flows (60 L/min) to rapidly relieve dyspnea and prevent muscle fatigue.^{29,30}

Aim

The primary goal of the study is to evaluate the efficacy of NHF versus conventional oxygen systems as regards treatment failure (as defined below) and respiratory parameters [respiratory rate, PaO_2 / (fraction of inspired oxygen) FiO_2 , peripheral oxygen saturation (SpO_2), use of accessory muscles, and dyspnea and comfort as regards the technique of respiratory support by using a visual analogue scale (VAS) after the extubation of cardiac surgery patients. An additional major goal of the study is to compare two different initial NHF flows of 60 L/min and 40 L/min, intensive care unit (ICU) Length of Stay, Hospital Length of Stay, rates of ICU re-admission and re-intubation and any other respiratory / non-respiratory complications and adverse events. The rate of failure of the initial treatment will be determined as the primary study outcome.

Methods

This is a prospective, non-blinded, randomized study in post-extubated cardiac surgery patients. The study population will consist of three patient groups: The first group (Study Group 1) will include patients on NHF with initial settings of $\text{FiO}_2=0.6$ and gas flow=60L/min. The second group (Study Group 2) will include patients on NHF with initial settings of $\text{FiO}_2=0.6$ and gas flow=40L/min. In the third group (control group) all patients will receive oxygen therapy according to the standard practice of our cardiac ICU department, i.e., Venturi mask with $\text{FiO}_2=0.6$ and flow of 15 L/min.

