Following extubation, patients will be randomly assigned to Study group 1 or 2, or to Control group at 1:1:1 ratio. Blocks of 3 numbers will be consecutively drawn from a sequence of 99 unique random numbers (range, 1-99). Random numbers will be generated by using Research Randomizer version 4.0 (www.randomizer.org). Upon patient enrollment, attending investigators will receive text message on their mobile phone devices. The text message will display the patient's code number and group.

Patient monitoring and data collection

Continuous patient monitoring will include electrocardiographic lead II, intra-arterial pressure, SpO₂, and respiratory rate.

Data on patient characteristics, including the European System for Cardiac Operative Risk Evaluation (EUROSCORE) II will be collected at baseline. Data collection time points for SpO₂, respiratory rate, PaO₂/FiO₂, comfort with respect to dyspnea and respiratory support modality (VAS score^{34,35,36}), accessory muscles' use, arterial pressure and heart rate, vasopressor support, and core body temperature will be as follows: within 30 min of extubation (baseline) and at 1, 2, and 4 hours, and every 4 hours onwards until 48 hours postextubation. Fluid balance of the first 24 and 48 hours postextubation will be recorded as well.

Adverse events/clinical course complications (e.g. hypoxemia and/or need for re-intubation, arrhythmias such as atrial fibrillation, occurrence of delirium,^{37,38,39,40,41} epileptic seizures, surgical re-exploration due to bleeding, ICU readmission, chest wound infection), and any patient discomfort/intolerance related to HFNC will also be recorded.

Management of respiratory support

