Secondary: 1] Successful maintenance of an SpO₂ of >92% and a respiratory rate of 12-29 breaths/min at the specified time points of follow-up; the term "successful" corresponds to the absence of any escalation of respiratory support above its initially specified level for each one of the Study groups and the Control group; 2] PaO₂/FiO₂ at the specified time points of follow-up; 3] Any use of accessory respiratory muscles at the specified time points of follow-up; and 4] Patient comfort as regards dyspnea, and patient tolerance of NHF support according to a VAS score.

Additional: 1] Length of cardiothoracic ICU stay; 2] Length of hospital stay; 3] ICU and in-hospital mortality; and 4] Adverse events (e.g. hypoxemia and/or need for re-intubation, arrhythmias such as atrial fibrillation, occurrence of delirium, epileptic seizures, surgical re-exploration due to bleeding, ICU readmission, chest wound infection), and any patient discomfort/intolerance related to NHF.

Sample Size and Power Analysis

The proposed sample size is based on a formal power calculation, i.e. an *apriori* power analysis, which is an efficient method of controlling statistical power before a study is actually conducted; for power analysis, G*Power 3 software was used.⁴⁴ We predict a treatment failure rate of 15% in the 2 Study groups (10% in Study group 1 and 20% in Study group 2) and a failure rate of 51% in the Control group. The predicted NHF-to-control treatment failure ratio of 0.29 corresponds to the lower limit of the 95% confidence interval (CI) of a previously determined "NHF vs. Control" odds ratio for support escalation.²⁵ For alpha=0.05 and power=0.80, 63 patients (n=21 per group) will be required. However, we cannot exclude a potential risk for dropouts and/or missing data. To compensate for such a risk, we propose the ultimate enrolment of 99 patients (i.e. n=33 per group), in order to achieve an alpha value of 0.05, a power of 0.96, and a "safety margin" of 57% as regards possible dropouts and/or missing data. The predicted study enrollment rate is 40-50 patients per year.

Interim Analysis and Data Monitoring

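### The VAS outcome is defined as both breathing comfort and tolerance of the support device, but the visible rating SOP asks only about breathing, so device tolerance has no graded score

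*Combined protocol and SAP*

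**What the plan says.** Four places in the protocol describe what the VAS is meant to capture.

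- **Aim:** "dyspnea and comfort as regards the technique of respiratory support by using a visual analogue scale (VAS").
- **Patient monitoring and data collection:** "comfort with respect to dyspnea and respiratory support modality", rated within 30 min of extubation, at 1, 2 and 4 hours, and then 4-hourly to 48 hours.
- **Follow-up description preceding the Study Eligibility Criteria list:** the same pairing, "comfort as regards dyspnea and respiratory support modality [visual analogue scale (VAS) score".
- **Outcome measures, secondary outcome 4:** "Patient comfort as regards dyspnea, and patient tolerance of NHF support according to a VAS score".

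The SOP for the rating of the level of breathing comfort then gives the bedside instruction, a single question: "How would you rate the level of your breathing comfort starting from 0". The lower anchor is "maximum discomfort – feeling unable to breathe"; the upper anchor, 10, describes effortless, regular breathing. The SOP refers to a scale displayed beneath the text.

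The Statistical Analysis Plan names one VAS comfort score, to be analysed by a linear mixed model with group, time and their interaction as fixed factors and patient as a random factor.

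Outside the VAS, discomfort or intolerance related to nasal high flow (NHF) is to be recorded alongside adverse events. It appears both under data collection and under the additional outcomes.

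**The concern.** The outcome definition and the instruction that staff follow do not match. A patient may breathe easily and still find the cannula, the heat or the flow hard to bear; another may accept the device while short of breath. On a scale anchored only on breathing, the first patient should score near 10 and the intolerance would not show.

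This bears on a main question of the trial. Comparing initial flows of 60 and 40 L/min is a stated major goal. The background gives better tolerance as the argument for starting lower, and faster relief of dyspnea as the argument for starting at the maximum. The single question measures the dyspnea side of that trade-off and leaves the tolerance side without a graded score. A rating not asked for at the bedside cannot be recovered later.

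**Working it through.** No power, alpha or event figure enters this point, and the plan states no figure to reproduce. The check sets the texts side by side.

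**Constructs specified for the VAS: two.** The Aim separates dyspnea from comfort with the technique. The two data-collection descriptions name comfort with regard to dyspnea and with regard to the support modality. Secondary outcome 4 names dyspnea comfort and tolerance of NHF. Because the pairing recurs in four places, it is unlikely to be a slip.

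**Questions in the visible SOP: one.** The title concerns breathing comfort, the question is introduced in the singular, and both anchors refer to breathing. Nothing in the visible wording asks about the cannula, mask, flow, heat or tolerance.

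**VAS variables in the Statistical Analysis Plan: one.** No separate tolerance score is named.

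So 2 constructs are specified, with 1 question and 1 variable. The question and anchors match the dyspnea construct, which leaves the tolerance construct without a scored item.

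**Who is affected.** Secondary outcome 4 limits tolerance to NHF: 2 groups × 33 = 66 of the 99 planned patients. The data-collection texts refer to the support modality at follow-up points that apply to every group, which would mean 3 × 33 = 99. The documents do not reconcile these two scopes.

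**How often.** The scheduled ratings are 4 early ones (30 min; 1, 2 and 4 h) plus (48 − 8)/4 + 1 = 11 from 8 to 48 h, so at most 15 per patient. Fewer will be obtained in practice, because 4-hourly collection stops at mechanical ventilation or ICU discharge within 48 hours.

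**The case against.** The strongest reply is that the plan may intend one combined score. The data-collection texts attach one VAS score to the paired phrase, secondary outcome 4 also speaks of a single score, and the SOP and Statistical Analysis Plan agree with each other. That is a fair reading of the intention. It does not remove the mismatch, because the anchors define the score by breathing alone, so it cannot stand for tolerance of the device.

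Second, the displayed scale is not in the text available for review, and the study forms mentioned under Interim Analysis and Data Monitoring could not be seen. Either might carry a second item. This stands as a limit on certainty, although the SOP's single question, its title and anchors, and the single analysis variable all point to one item.

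Third, a reader might infer that device tolerance goes unrecorded altogether. The documents do not support that. NHF-related discomfort or intolerance is to be recorded, and nothing says whether it is elicited or volunteered. Treatment failure includes crossover prompted by respiratory distress and discomfort, including a move from NHF to the Venturi mask, so clinically important intolerance may also enter the primary outcome. Nor is mask discomfort excluded: the adverse event SOP (section 2.1) counts unfavourable changes in symptoms as adverse events, whatever the group. These routes do not supply a graded rating, and only NHF intolerance is named, so they cannot stand in for the VAS outcome.

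**Conclusion.** The concern holds for the visible text. Followed as written, the SOP and Statistical Analysis Plan yield a breathing-comfort score but no graded VAS score for tolerance of, or comfort with, the support device, although four places say the VAS covers it. The 60 versus 40 L/min comparison therefore lacks a graded tolerance measure, and a favourable breathing score could not be reported as good tolerance.

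The size is limited: one component of one secondary outcome, in 66 planned patients on the NHF-only wording or 99 on the modality wording. The primary outcome and sample size are unaffected. The conclusion assumes that neither the displayed scale nor the study forms contain a second item. A reader might go further and count every planned patient as certain to lack any tolerance information. The unseen scale and forms, the NHF-only wording and the unscored recording of intolerance rule that out.

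**What to change.** First check the displayed scale and the study forms. If they hold no device item, take one of two routes.

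1. **Measure it.** Add to the rating SOP a second 0-10 VAS question on comfort with the oxygen device in use, with its own anchors, at the same time points. Ask it in all three groups, consistent with the modality wording, and reconcile the NHF-only wording of secondary outcome 4. Name it in the Statistical Analysis Plan as a separate variable, analysed with the linear mixed model already planned. The cost is one short question per assessment (at most 15 per patient) and one case report form field.
2. **Do not claim it.** Remove tolerance and modality from the VAS wording in the Aim, both data-collection descriptions and secondary outcome 4. Report breathing comfort only, and present recorded intolerance descriptively. The cost is a few deleted phrases and the loss of any graded statement on tolerance.

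The first is preferable if tolerance is to inform the choice between the two flows.

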5.5. Evaluation of causality

5.6. Evaluation of expectedness

6. REFERENCES

1. PURPOSE

This Standard Operating Procedure (SOP) describes the procedure to be used by the investigator for the recording, management and reporting of Adverse Events (AEs), Adverse Reactions (ARs), Serious Adverse Events (SAEs), Suspected Serious Adverse Reactions (SSARs) and Suspected Unexpected Serious Adverse Reactions (SUSARs) which occur in subjects participating in the non-commercial, academic, investigator-initiated, prospective, parallel-group, randomized, unblinded OPTICAR study.

2. BACKGROUND

This SOP is written in accordance with Good Clinical Practice (GCP) requirements as previously outlined in Directives 2001/20/EC and 2005/28/EC, and currently supported by the CLINICAL TRIALS REGULATION (EU) No 536/2014.

2.1. DEFINITIONS

The following definitions have been adapted:

Adverse Event

Any untoward medical occurrence in a patient or clinical trial subject administered an intervention (INT) and which does not necessarily have a causal relationship with this treatment.

Therefore, an AE can be any unfavorable or unintended change in the structure (signs), function (symptoms) or chemistry (laboratory data) in a subject to whom an INT has been administered, including occurrences which are not necessarily caused by or related to the INT.

Adverse Reaction

All untoward and unintended responses to the use of an INT related. This definition also covers errors and uses outside what is foreseen in the protocol, including misuse and abuse of the INT device. The definition implies a reasonable possibility of a causal relationship between the event and the INT. This means that there are facts (evidence) or arguments to suggest a causal relationship.

Serious Adverse Event and Serious Adverse Reaction

Any adverse event or reaction in a trial subject that:

- (a) results in death; or
- (b) is life threatening; places the subject, in the view of the investigator, at immediate risk of death from the experience as it occurred (this does not include an adverse experience that, had it occurred in a more severe form, might have caused death); or
- (c) requires hospitalization or prolongation of existing hospitalization;
- (d) results in persistent or significant disability or incapacity

Important Safety Issues

Important medical events that may not be immediately life-threatening or result in death or hospitalization but may jeopardize the subject or may require intervention (medical or surgical) to prevent one of the other outcomes listed in the definition above should also be considered serious. Such events might include:

1. An alarming adverse experience
2. Specific Adverse events and/or laboratory abnormalities which are listed in the trial protocol as critical to safety evaluations and requiring reporting.

Suspected Serious Adverse Reaction

An adverse reaction that is classed in nature as serious and which is consistent with the information about the INT device listed in the relevant reference documentation in the case of a licensed device being used within its licensed indication or in the Investigator's Brochure (IB) in the case of a licensed device being used outside its licensed indication.

Unexpected Adverse Reaction

An adverse reaction, the nature or severity of which is not consistent with the applicable product information.

Suspected Unexpected Serious Adverse Reaction

An adverse reaction that is classified in nature as both serious and unexpected.

2.2 OTHER SAFETY ISSUES CONSIDERED TO BE SERIOUS IN THE CLINICAL TRIAL.

Events which may materially alter the current benefit-risk assessment of an investigational INT or which could be sufficient to consider changes in INT administration or in the overall conduct of the trial may fall into the category of 'Other Safety Issues' and be considered as serious events which will require reporting to the sponsor in a letter headed Safety Report:

- a. An increase in the rate of occurrence or a qualitative change of an expected serious adverse reaction, which is judged to be clinically important,
- b. Post-study Suspected Unexpected Serious Adverse Reactions (SUSARs) that occur after the patient has completed a clinical trial and are reported by the investigator to SEC,
- c. New events related to the conduct of the trial or the development of the IMPs and likely to affect the safety of the subjects, such as:
 - 1) A Serious Adverse Event (SAE) which could be associated with the trial procedures and which could modify the conduct of the trial,
 - 2) A significant hazard to the subject population such as lack of efficacy of an IMT used for the treatment of a life-threatening disease,

Recommendations of the Data Monitoring Committee (DMC), if any, where relevant to the safety of the subjects.

An "Other Safety Issue" can also fall into the category of Urgent Safety Measures. Please refer to the Standard Operating Procedure for the Recording and Reporting of Deviations, Violations, Potential Serious Breaches, Serious Breaches and Urgent Safety Measures.

2.3 SEVERE ADVERSE EVENT OR REACTION

The term "severe" is often used to describe the intensity of an event or reaction (e.g. mild, moderate or severe) and should not be confused or interchanged with the term "serious".

2.4 KEY RESPONSIBILITIES FOR THE INVESTIGATOR

This section describes the key responsibilities of the investigator, further delegation of these responsibilities to other team members must be documented on the trial delegation log.

1. The principal investigator (PI) must further ensure that the team are all familiar with the appropriate use of the INT, as described in the protocol.
2. Adverse Event (AE) Recording: All AEs must be recorded in the medical records (if source data) and/or the patient case report form (CRF), Serious Adverse Event (SAE) forms and AE logs as described in the protocol.
3. AE Assessment: The PI / investigator(s) must assess each event for **seriousness, expectedness and causality** using the appropriate documentation (protocol and safety reference document).
4. Trend/signal analysis: The PI must ensure the AE log is reviewed regularly. This can be performed by the PI alone or reviewed collectively at trial meetings. These reviews need to be documented.
5. SAE Reports: The PI must ensure that initial and follow-up SAE reports are sent to the Scientific and Ethics Committee (SEC), according to the protocol.
6. Confidentiality: The PI must always maintain subject confidentiality.
7. Urgent Safety Measure: The PI / investigator(s) may take appropriate urgent safety measures to protect clinical trial subjects from any immediate hazard to their health and safety. This may be taken immediately. However, following the measure the PI / investigator must follow the SOP on "Deviations, serious breaches and urgent safety measures".

